## 4.2 Study Population

### 4.2.1 Selection Criteria

Subjects will be screened for eligibility from the available pool of candidates with post-stroke shoulder pain seen by the Investigator. The specific inclusion and exclusion criteria are listed in **Table 2** below. The total number of subjects and sites we are requesting for this study are listed immediately following the Inclusion/Exclusion Criteria and are presented in **Table 3**.

**Table 2.** Inclusion/Exclusion Criteria

Inclusion criteria	Exclusion criteria

At least 21 years old

≥6 months after the stroke that caused shoulder pain

Subject failed or did not tolerate at least two conservative therapies for a total period of at least 6 months since the onset of post-stroke shoulder pain.

Shoulder pain as indicated by a score of ≥4 on the Brief Pain Inventory (BPI3)

Upper extremity hemiplegia (No shoulder abduction, shoulder abduction in synergy or if

	

Evidence of joint or overlying skin infection of the affected limb

Taking any opioid medication (or Tramadol) for shoulder pain OR for any other chronic pain condition

Intra-articular or sub-acromial steroid injections or botulinum toxin injections to the affected shoulder in the previous 12 weeks

History of arrhythmia with hemodynamic instability, such as ventricular tachycardia, supraventricular tachycardia and rapid ventricular response atrial fibrillation OR valvular heart disease including artificial valves


isolated movement is present, shoulder abduction <math>\leq 4/5</math> on Medical Research Council (MRC) scale)
 
 
• Cognitive ability to fulfill study requirements based upon a score of <math>\geq 24</math> on the Mini Mental Status Exam (MMSE)
 
• Ability to appropriately rank pain on a Numeric Rating Scale (based upon the Investigator's determination of the subject's ability to rank pain)
 
• Availability of a reliable adult who can check the skin and assist the subject with the study protocol
 
• Able and willing to take part in study
 
 
ADDITIONAL CRITERION FOR THE IMPLANT STAGE
 
In addition to continuing to meet the above inclusion criteria (with the necessary pain score already having been confirmed at a Trial Stage Follow-up Call), subjects must:
 
 
• Be a Trial Stage Success AND
 
• Have a clinically significant return of pain as defined by an increase in BPI3 score of at least 2 points (compared against the BPI3 score at Visit 5) resulting in a BPI 3 score of at least 4 within 6 months of the end of the Trial Stage that is sustained for at least two consecutive weeks.
 
	
 
• Evidence of non-stroke related shoulder pathology with continuing symptoms (such as pathology related to a traumatic injury, tumor, or infection)
 
• Bleeding disorder OR INR <math>>3.0</math> for those on warfarin
 
• Unable, per the prescribing physician, to stop antiplatelet medications [e.g., aspirin, clopidogrel (Plavix)] and/or anticoagulants for at least 7 days prior to SPR implantation.
 
• Receiving outpatient physical or occupational therapy for shoulder pain
 
• History of recurrent skin infections
 
• Compromised immune system based upon medical history (i.e., HIV/AIDS, actively taking or recently completed immunosuppressive therapies such as chemotherapy or radiation of the head/neck, congenital immunodeficiency, or any other cause for compromised immune system documented in the medical history)
 
• Medical instability that may interfere with ability to participate in a clinical trial as determined by the Principal Investigator
 
• Severely impaired communication skills (receptive or expressive) as determined by the Principal Investigator
 
• Confounding conditions such as ipsilateral upper limb lower motor neuron lesion, Parkinson's Disease, SCI, traumatic brain injury, MS, or complex regional pain syndrome
 
• Uncontrolled seizures (<math>>1</math> per month for 6 months)
 
• An implanted electronic device
 
• Allergy to skin surface electrodes and/or medical-grade adhesive tapes.
 
• Allergy to local anesthetic agents such as lidocaine or previous reaction to Monitored Anesthesia Care (MAC)
 
• Pregnant
 
• Prisoners, minors, legally incompetent people, unconscious patients, house staff, or students
 

--	---

We are requesting the following number of subjects and sites for our Pilot Study (**Table 3**).

**Table 3.** Subject and Site Totals Requested for Pilot Study

Description	Number of Subjects/Sites
-------------	--------------------------

Total Number of Subjects enrolled for eligibility (evaluation of minimum pain score on BPI3 inclusion criterion; INR testing in selected individuals, and pregnancy test)	Approximately 90
Total Number of Subjects undergoing SPR Trial Stage (Smartpatch System)	Up to 45
Total Number of Subjects with SPR Implant Stage (implantation of IPG and Implantable Lead)	Approximately 18
Number of Pilot Stage Investigational Sites	Up to 5 sites

#### 4.2.2 Subject Disposition

Subject disposition in this study will be characterized as described in **Table 4** below.

**Table 4.** Subject Disposition Categories (continued on following page)

Disposition Category	Description
Screened Subjects	All subjects who are screened for potential study participation will be listed on a screening log. Those subjects who are excluded will be listed along with their reason for exclusion. Screened subjects include those individuals that were screened from record searches as well as those that came to the clinic, signed a consent form, and underwent further screening for eligibility.
Screen Failures (2 Levels)	
Any subject who signs an Informed Consent and does not receive a SPR Trial Stage System will be dispositioned as a screen failure as follows:
 
Level 1: Subjects who do not meet the pain intensity criteria (<math>\geq 4</math> on the baseline BPI3).
 
Level 2: Subjects who do not meet the criteria for the INR score or pregnancy test.
 
[REDACTED]

Enrolled	Subjects who sign a consent form AND meet all eligibility criteria will be assigned a study ID and will be considered “enrolled” at that time. Any subject who has a lead replaced will only be counted once against total study enrollment.
SPR Trial Stage Failure	Subjects who receive the SPR Trial Stage System but do not demonstrate at least a 2-point reduction on the BPI3 during the Trial Stage.
Withdrawn	Subjects who voluntarily withdraw their study participation or are lost to follow-up will be categorized as withdrawn.
Terminated	Subjects who are prematurely terminated from the study by the Investigator. Termination forms will capture the reason for study termination.
Completed	
Subjects who are Trial Stage successes and do not report a clinically significant and sustained return of pain within 6 months of the Trial Stage.
 
OR
 
Subjects who complete both the SPR Trial Stage and the Implant Stage and complete all follow-ups through the 36-month visit.

[figure not shown]
#### **4.2.2.1     Subject Disposition following infection of Percutaneous or Implantable Leads**

Subjects with infections related to the implanted electrodes will be treated and dispositioned according to the severity of the infection and the SPR stage (Trial or Implant). In the Trial Stage, subjects who develop a mild infection will receive the appropriate medical treatment (such as administration of antibiotics or wound cleansing) and the Smartpatch Lead will remain in the shoulder. An infection is considered to be “mild” when: 1) it is a superficial infection that does not involve a fever 2) it can be treated with topical antibiotics and/or appropriate cleansing agents and 3) it does not place the subject at risk for a deep tissue infection. These subjects will continue in the study.

Subjects who develop a moderate or severe infection (i.e any infection beyond what is described as mild above) during the Trial Stage or any infection of the components (Implantable Lead or IPG) during the Implant Stage will have the SPR System removed. These subjects will be followed until resolution of the infection. Upon resolution, the subject will be terminated from the study.

#### **4.3 Justification for the Study Design**

This study is a prospective non-randomized multicenter case series pilot study.

---

#### **4.3.2 Justification of Treatment Duration**

Our study design includes a 6-week SPR Trial Stage with 3-weeks of Sham Stimulation and 3-weeks of Trial Stage Stimulation. Previous [REDACTED] studies (Chae et al, 2005, Yu et al, 2004) used 6-weeks of stimulation, however further analysis of this data showed that the majority of pain reduction for the treatment subjects occurred during the first three weeks of stimulation. We anticipate that 3-weeks of SPR Trial Stage stimulation will be sufficient to determine which subjects will benefit from long-term therapy with the SPR System. Similarly, we anticipate that 3-weeks of sham stimulation will be sufficient to give us an indication of whether subjects experience a placebo effect from having the SPR Trial Stage System present. [REDACTED]

If a subject reports pain relief during the SPR Trial Stage but experiences the specified return of pain, he or she will advance to the SPR Implant Stage. As described above, a post-hoc analysis of the previous randomized controlled trial on [REDACTED] stimulation (Chae et al, 2005), demonstrated that stroke survivors who are treated later after stroke onset responded to a 6-week stimulation therapy but had a return of pain once the therapy was concluded. However, some stroke survivors who are treated soon after stroke onset may experience benefit from a temporary therapy for at least 12-months. Therefore, we are proposing that pain must return in order to warrant a fully implantable system.

#### 4.4 Study Endpoints

##### 4.4.1 Primary Endpoints

###### 4.4.1.1 Reduction in pain intensity (Brief Pain Inventory)

The primary endpoint of the study is reduction in pain intensity over the past week as measured using the 11-point numerical rating scale of the Brief Pain Inventory (BPI3). The BPI is a widely used and validated assessment designed to measure pain intensity and the interference of pain on daily activities and moods (Cleeland and Ryan, 1994).

The BPI is recommended by the Initiative on Methods, Measurement, and Pain Assessment in Clinical Trials (IMMPACT) panel and has demonstrated validity and reliability across many cultures and languages (Cleeland and Ryan, 1994; Tan et al., 2004; Dworkin et al., 2005). The IMMPACT panel was assembled to develop consensus recommendations to improve and standardize the design and conduct of clinical trials involving treatments for pain. Invited participants included academic centers, regulatory agencies, the National Institutes of Health, the US Veterans Administration, and industry representatives. In addition, the BPI has been used in many chronic pain studies, including those for post-stroke shoulder pain, which demonstrated a significant reduction in pain intensity as compared to a standard of care control (Chae et al., 2005; Yu et al., 2004).

All subjects will be evaluated for a reduction in their worst pain intensity in the previous week (BPI3) at several key study visits: (1) at the completion of the 3-week sham period (Visit 4) to evaluate the placebo effect; (2) at the completion of the 3-week SPR Trial Stage stimulation period (Visit 5) to determine if the subject has met the criteria to be a Trial Stage Success; (3) during the Trial Stage follow-up period to assess for Implant Stage eligibility, and (4) at 3-weeks (Visit 8), 6-weeks (Visit 9), 12-weeks (Visit 10), 6-months (Visit 11), 9-months (Visit 12), 12-months (Visit 13), 24-months (Visit 14), and 36 months (Visit 15) following

the initiation of IPG Stimulation to determine efficacy of the implantable system. The BPI will be administered with stimulation turned off (for at least one hour prior to the study visit) and subjects will be instructed to focus on their shoulder pain when responding to the questions presented in the BPI.

The proportion of subjects achieving success in each stage will be calculated. A 2-point reduction in pain intensity is considered to be the minimum clinically important difference (MCID) on a 0-10 pain numeric rating scale (Farrar et al., 2001). Primary efficacy of the Trial Stage therapy will be determined at the end of the Trial Stage. Primary efficacy of the Implant Stage will be determined at the 12-week post-IPG Stim On follow-up visit. A subject will be considered a Trial Stage Success if he/she achieves at least a 2-point reduction in post-stroke shoulder pain intensity score in the BPI Pain Intensity Question #3 (BPI3) at the end of the Trial Stage (Visit 5) relative to end of the placebo period or baseline (Visit 4 or Visit 1), whichever is lower OR reports a BPI3 score of zero at the end of the Trial Stage.

In addition, the average reduction in pain intensity across all subjects during each stage will be analyzed.

#### **4.4.1.2 Safety**

The primary safety endpoint is the occurrence and type of device related adverse events (AEs). All AEs that occur during the study will be documented. Specific details regarding any observed AE will be collected on an AE Form and will be followed to resolution. The severity of each Adverse Event will be collected as well as its relationship to the SPR System. Any necessary treatment or intervention required and the resolution status of the adverse event will also be documented. AEs will be tabulated and summarized at the conclusion of the study. Additional details on the monitoring and adjudication of AEs is described in Section 11 (Data Safety Monitoring Board).

#### **4.4.2 Secondary Endpoints**

Several secondary endpoints are being collected to gain a better understanding of what effect, if any, the SPR System may have on each measure. We intend to evaluate these instruments (described below) to determine their usefulness in our future larger pivotal study on the 2-stage implantable system.

Similar to the primary endpoint, all secondary endpoints will be assessed when stimulation is off (for at least one hour prior to the study visit). Stimulation therapy is administered for 6 hours per day and thus, it is off for the majority of the day. All endpoints will be measured when stimulation is off (for at least one hour prior to the study visit) such that the overall impact of daily stimulation on the subjects' primary and secondary endpoints can be assessed, rather than the potential immediate effect of having stimulation on.

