#### **4.4.2.2 Pain-free passive range of motion (ROM)**

Pain will also be assessed using the pain-free shoulder external rotation ROM assessment. Following stroke, the shoulder often demonstrates a decreased range of motion (Fugl-Meyer, 1980). This decrease in ROM is associated with shoulder pain (Bohannon et al., 1986). In order to measure the pain-free passive ROM, stimulation will be turned off (for at least one hour prior to the study visit) [REDACTED]

Assessing the pain-free passive ROM is common in both clinical research and clinical practice as an objective measurement of pain (Chantraine et al., 1999; Faghri et al., 1994; Chae et al., 2005; Renzenbrink and IJzerman, 2004). Results will be analyzed to determine what impact, if any, the SPR System has on pain-free passive ROM. We expect no worsening of the pain-free ROM and will review the results to determine the usefulness of this measure for our pivotal study on the implantable system.

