#### **4.4.2.3 Medical Outcomes Study Short Form (SF-36v2)**

It is important to measure the health-related quality of life (HRQOL) in chronic pain studies, as pain is known to impact daily activities (Dworkin et al., 2005). The SF-36v2 (Ware and Sherbourne, 1992) will be administrated throughout the study to assess the change in HRQOL between the pre- and post-treatment periods. The SF-36v2 is a generic health survey designed to assess basic physical functioning and emotional well-being regardless of the disease or treatment. The 36 items are grouped into eight domains: physical functioning, role limitations due to physical problems, social functioning, bodily pain, general mental health, role limitations due to emotional problems, vitality, and general health perceptions. The SF-36v2 is the most commonly used generic measure of HRQOL and has shown acceptable reliability and validity in stroke populations (Anderson et al., 1996; Dorman et al., 1998). Results of the SF-36v2 will be analyzed to determine the instrument’s ability to detect changes resulting from

SPR therapy [REDACTED]

[REDACTED] In particular, results will be evaluated to ensure that there is no worsening of HRQOL.

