#### 5.4.3 Secondary Endpoint Analysis

As with the primary endpoint, we will analyze what effect, if any, the treatment has on pain interference (BPI9), Pain Free Passive Range of Motion, SF-36v2, BDI-II, the Patient Global Impression of Change scale, the SULCS, and subject satisfaction. QST testing is optional and thus an analysis will be completed if sufficient data are gathered.

Pain interference (BPI9), Pain Free Passive Range of Motion, SF-36v2, and BDI-II, the SULCS, and QST Testing are collected at the End of Trial Stage, 3-weeks, 12-weeks, 6-months, 9-months, and 12-months post IPG Stim ON. These secondary endpoints will be compared to the End of Sham. In addition, the pain interference (BPI9) is also collected at 6-weeks, 24-months and 36-months post IPG Stim ON and will be compared to End of Sham. As with the primary endpoints, subjects demonstrating a negative placebo effect for secondary endpoints will be compared to Baseline.

Results of the Patient Global Impression of Change scale and the subject satisfaction survey will be independently summarized to assess for a positive response indicating overall subject satisfaction with the system and therapy.

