#### **6.1.2.4 Overall study success**

Overall study success is defined by the success rate across all subjects participating in each stage, and is expected to exceed the historically observed success rate █ based upon previous and ongoing studies that demonstrated a █ success rate among subjects treated with stimulation therapy (Yu et al., 2001a; Chae et al, 2005; Chae et al., 2013; Wilson et al., 2014; as well as the present study and an unpublished randomized controlled trial).

A test of significance will be carried out to test the null hypothesis that the success rate █ or less versus the alternative that the true success rate exceeds █. In addition, a 95% confidence interval for the true success rate will be reported with the expectation that the lower limit of the interval will exceed █

All treatment failures, including any subjects who had an Implant Stage system removed due to an adverse event, will also be analyzed as part of this analysis.

Finally, a logistic regression will be reported, treating subject success as the binary outcome and baseline BPI as a possible explanatory variable. Other subject characteristics, such as time post-stroke, cortical vs. subcortical, right vs. left affected shoulder, and subluxation versus non-subluxation will be examined via a covariate analysis.

Secondary endpoints will be assessed using non-parametric tests. The Wilcoxon signed-rank test will be used to examine the difference of each endpoint for each subject. We will also investigate the mean improvement by reporting the results using a one-sample t-test.

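### The secondary instruments are piloted for their usefulness in the pivotal study, but the only tests named for them are of overall change, which cannot show whether an instrument moves with pain relief

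*Combined protocol and SAP*

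**What the plan says.** Section 4.4.2 states two purposes for the secondary endpoints: to learn what effect the system has on each measure, and to evaluate the instruments themselves ("We intend to evaluate these instruments (described below) to determine their usefulness in our future larger pivotal study on the 2-stage implantable system"). Section 4.4.2.2 repeats the second purpose for pain-free range of motion: the sponsor "will review the results to determine the usefulness of this measure for our pivotal study on the implantable system". Section 4.4.2.3 says SF-36v2 results will be analyzed for the instrument's "ability to detect changes resulting from" the therapy; the text that follows is redacted. Section 4.4.2.9 states the hypothesis that less shoulder pain goes with less arm impairment and better daily activities on the SULCS.

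For the analysis, Section 5.4.3 sets the reference: "These secondary endpoints will be compared to the End of Sham", except that "subjects demonstrating a negative placebo effect for secondary endpoints will be compared to Baseline". Section 6.1.2.4 names the tests: "The Wilcoxon signed-rank test will be used to examine the difference of each endpoint for each subject" and "We will also investigate the mean improvement by reporting the results using a one-sample t-test". Section 6.2 repeats the analysis at 36 months for the endpoints still collected. PGIC and satisfaction are handled differently: "Results of the Patient Global Impression of Change scale and the subject satisfaction survey will be independently summarized to assess for a positive response".

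**The concern.** A test of overall change answers the first purpose, whether scores moved on average. It does not answer the second. Its p-value depends on the number of subjects, the share who respond and any general trend after the reference visit. It takes no account of whether the score moved in subjects whose pain fell and stayed still in the others.

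There is no concurrent control group, so drift after Visit 4 from time, repeated testing or attention cannot be told apart from a response to therapy. In the other direction, an instrument that follows pain closely can show little average change if few subjects respond. The pilot could then end with a column of p-values and no answer on which instruments respond, and with no test of the one association it sets out as a hypothesis.

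**Working it through.** **Step 1: aims beside analyses (visible text).**

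| Aim | Analysis found |
|---|---|
| Usefulness of the instruments for the pivotal study (4.4.2), repeated for ROM (4.4.2.2) | Tests of overall change; no criterion for usefulness |
| SF-36v2 ability to detect change from therapy (4.4.2.3) | Same tests; nearby text redacted |
| SULCS change associated with pain reduction (4.4.2.9) | No association analysis in 5.4.3 or Section 6 |
| QST subgroups by response (4.4.2.8, optional) | Analysis if data suffice (5.4.3); no method for the subgroups |

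Two analyses come close. The logistic regression in 6.1.2.4 explains success by baseline BPI and subject characteristics, not by change in an instrument. The comparison of the sham period with the stimulation period in 6.1.2.1 covers BPI3 only.

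**Step 2: can the named tests discriminate?** The documents give no power or effect size for the secondary instruments, so there is no figure of theirs to reproduce. Inputs: n = 45 (Table 3, an upper limit). Assumed: 60% Trial Stage successes, change SD of 1 within each outcome group, two-sided 5% level. Instrument A moves 0.8 SD in successes and 0 in failures. Instrument B ignores pain and drifts 0.6 × 0.8 = 0.48 SD in everyone. B's drift is set to A's mean on purpose.

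One-sample t-test, noncentrality = √n × mean / SD:
- A: SD = √(1 + 0.6 × 0.4 × 0.8²) = √1.1536 = 1.074; 6.708 × 0.48 / 1.074 = 3.00; power about 83%.
- B: 6.708 × 0.48 / 1 = 3.22; power about 88%.

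Simulating both planned tests gives 82–84% for A and 87–89% for B.

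Success versus failure, 27 against 18 subjects:
- A: 0.8 / √(1/27 + 1/18) = 0.8 / 0.304 = 2.63; power about 73%.
- B: no group difference, so about 5%.

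With success rates of 50–70%, the planned tests give 66–93% (A) and 73–96% (B); the contrast gives 66–74% and 4–6%.

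A second model gives the same picture. With n = 45 and a mean change of 0.5 SD, the signed-rank test rejects in 90% of runs when instrument change is unrelated to pain change and in 89% when the correlation is 0.5; the Spearman test rejects in 5.5% and 92%. If the correlation is 0.6 but mean change is zero, the signed-rank test rejects in about 5% and Spearman in 99%.

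**Step 3: the plan's own reference.** Step 2 uses plain visit-to-visit change. The rule in 5.4.3 measures change from the better of Baseline and End of Sham, which makes improvement harder to show. Under that rule, with 25–100% of the change variance assumed to be visit error and no drift during sham, significant improvement appears in roughly 6–40% of trials for A and 8–49% for B. The levels fall a long way, but the two instruments are still not separated.

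**Step 4: precision of an anchored analysis.**
- AUC for A: Φ(0.8/√2) = 0.71. The Hanley–McNeil variance with 27 and 18 subjects is about 0.0058, so SE = 0.076 and the 95% half-width is 1.96 × 0.076 = 0.15.
- Smallest correlation with 80% power: tanh((1.96 + 0.84)/√(n − 3)) = 0.41 at n = 45 and 0.62 at n = 18.
- 95% CI around r = 0.5: 0.24 to 0.69 at n = 45; 0.04 to 0.78 at n = 18.

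**The case against.** The first stated purpose is simply to see what effect the system has, and a test of change serves it. Usefulness is not defined, and Section 4.4.2.3 speaks of change from therapy, not from pain relief. Depression, quality of life and range of motion are separate domains, so choosing instruments by agreement with BPI3 would favor those that duplicate the primary endpoint. This stands: BPI3 agreement should not be the sole criterion.

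A reader might infer that every secondary endpoint is only tested against zero. The documents do not support that: PGIC and satisfaction are summarized, and SULCS and QST have stated aims tied to pain reduction or response. The gap there is a missing method, not a missing aim.

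A reader might also infer that any drift at all would make an instrument look useful. That goes too far. The End of Sham reference removes drift before Visit 4 for most subjects, and the negative-placebo rule requires Visit 1 to be compared with Visit 4. Drift after Visit 4 remains.

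Nor does any rule say that pivotal instruments will be picked by p-value, so adoption of the wrong instruments is a possibility, not a planned outcome. Redactions in Sections 4.4.2.3 and 4.4.2.5 (BDI-II) may hide instrument-specific criteria. Finally, the analysis could be added later, since the data are collected anyway. But prespecifying it costs little and keeps the choice of anchor from following the results.

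**Conclusion.** The concern holds in limited form. In the visible text, the only statistical tests named for these endpoints are of overall change. They cannot show whether an instrument moves with pain relief or drifts after Visit 4, and nothing visible tests the SULCS hypothesis. This follows from what a one-sample test uses and does not depend on the simulation.

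The percentages (about 83% against 88% for the planned t-test, 73% against 5% for the contrast) are illustrative. They rest on an assumed success share, effect size, SD and 5% level, and apply to plain change only; under the plan's reference rule the rates are much lower, though still not discriminating. The primary endpoint is unaffected. This is a cheap improvement that lets the pilot answer a question it sets itself.

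**What to change.** In Sections 5.4.3 and 6.1.2.4, for BPI9, pain-free ROM, each SF-36v2 domain, BDI-II and SULCS, add:

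- **(a)** the Visit 4 to Visit 5 change by Trial Stage success versus failure, with the between-group difference and 95% CI, and the rank correlation with BPI3 change over the same interval;
- **(b)** a within-subject comparison of change during sham (Visit 1 to 4) with change during stimulation (Visit 4 to 5), in line with what Section 6.1.2.1 does for BPI3;
- **(c)** the SD of change, for pivotal sample-size planning.

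State that (a) and (b) use plain visit-to-visit change instead of the reference rule in Section 5.4.3, and that the estimates will inform, not solely determine, the choice of pivotal instruments.

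The cost is analysis wording and a few tables, with no new visits or measurements. There are limits to state:

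- Estimates are imprecise at 45 subjects and more so at 18. SULCS will have fewer than the full Trial Stage number if subjects enrolled before it joined the protocol, because only later enrollees have a baseline (Section 4.5.1).
- Trial Stage success is judged against Baseline for subjects who worsened during sham, so the grouping and the Visit 4 to 5 change use different references for them. The rank correlation avoids this.
- Sham always comes first, so (b) cannot fully separate treatment from order. It is also noisier: the contrast Visit 5 − 2 × Visit 4 + Visit 1 carries 1 + 4 + 1 = 6 units of visit-error variance, against 2 for a simple change.
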